To develop our RESET intervention, we will modify the protocol of the aforementioned ASAT to target exercise sensitivity (vs. anxiety sensitivity) in ACS patients (vs. healthy adults), as well as use structured physical activity (vs. breathing into a paper bag) as a form of interoceptive exposure in home-based and community settings (Stage 1A: Intervention Development). We will then use an iterative human-centered design process to optimize the patient experience and maximize feasibility (Stage 1B: Feasibility). The purpose of this pilot study is to determine the feasibility (e.g., recruitment, adherence, fidelity), acceptability, and appropriateness of a RESET intervention in ACS patients. We will also explore pre- to post-intervention changes in exercise sensitivity and physical activity levels.

2. Study Design

An overview of the RESET pilot study design, including visits and research activity, is presented in Table 1. We will recruit **30** participants who survived an ACS event in the past 12 months. Participants will be contacted by research personnel via phone call to review the study, obtain verbal consent, and complete a brief set of screening questions to determine eligibility (Phone or Zoom Call Visit 1). Phone Call Visit 2 will include completion of **baseline questionnaires** and a **cardiac rehabilitation interview**. Phone Call Visit 2 can occur

Revised 1/26/2024 Page **2** of **7**

Table 1. Overview of Study Design			
Visit Type	Research Activity	Duration	Mode
Phone (or Zoom)	Participant consent and enrollment	15-30 mins	Phone
Call Visit 1			Zoom
Phone Call Visit 2	Pre-Intervention Preparation		Phone
	a. Baseline Questionnaires	20 mins	
	b. Cardiac Rehabilitation Interview	30 mins	
Video Visit 1	Intervention Setup	60-90 mins	Zoom
Video Visit 2	Intervention visit		Zoom
	a. Psychoeducation	30 mins	
	 b. Interoceptive exposure 	15 mins	
	c. Interoceptive counseling	10-20 mins	
Video Visit 3	Intervention visit		Zoom
	a. Interoceptive exposure	15 mins	
	b. Interoceptive counseling	10-20 mins	
Video Visit 3	Post intervention visit		
Continued	a. Post-intervention questionnaires	20 mins	Zoom or
			Phone
Phone Call 3	2. Exit Interview	30-45 mins	Phone

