at the time of enrollment (Phone Call Visit 1) or within 1-2 weeks after enrollment based on participant preference. The intervention setup video visit (Video Visit 1) will include download of the Fitbit app and setup of the Fitbit Inspire HR device, setup of the home environment. and а brief practice session to familiarize participants with intervention visits, which will include psychoeducation, brief, low-to-moderate intensity physical activity session (e.g., gradual six-minute [G6MW]), and interoceptive counseling. Participants will be

guided in setting up their walking course as well as positioning their device with Zoom so that study staff can monitor them as they walk. If the participant's home-environment is not conducive for proper monitoring of the G6MW, or they are uncomfortable displaying their home environment, they will be given the opportunity to complete the physical activity session by walking in place.

The RESET *intervention visits* (Video Visits 2-3) will include psychoeducation (in Video Visit 2 only), a brief, low-to-moderate intensity physical activity session (e.g., gradual six-minute walk [G6MW]), and interoceptive counseling. Each RESET intervention visit will occur once or twice per week based on participant preference. All video visits will be conducted with research personnel via Zoom, an encrypted, HIPAA compliant, web-based, video-conferencing application.

At the end of Video Visit 3, participants will be asked to complete *post-intervention questionnaires*. The post-intervention questionnaires will include the same set of baseline questionnaires plus additional surveys to rate the acceptability, appropriateness, and feasibility of the intervention sessions. Lastly, to elicit feedback on the RESET design and assess the participant's perceived barriers and facilitators to participating in the pilot study, the participant will also be asked to complete a 30-minute semi-structured *exit interview*, which will be completed on the telephone and will be audio recorded using the Zoom platform on a separate device with participants on speaker phone with research personnel.

3. Study Procedures

Eligibility Criteria: A total of 30 acute coronary syndrome (ACS) patients who report at least some fear of exercise will be offered an opportunity to enroll in the RESET study.

Patients will be included if they meet the following inclusion/exclusion criteria:

Inclusion Criteria:

- Age 18 years or older
- Speak and read English

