Pre-Intervention Preparation (Phone Call Visit 2 and Video Visit 1): A member of the research team will meet with the participant on a secure phone line to conduct a series of pre-intervention preparation components, which includes a set of baseline questionnaires and a cardiac rehabilitation interview (Phone Call Visit 2 [50-60 mins]). The interview will be audio recorded using the Zoom platform on a separate device with participants on speaker

phone with research personnel. Once the questionnaire and cardiac rehabilitation interview is concluded, research personnel will meet with the participant via the Zoom Video Visit platform to conduct intervention setup (Video Visit 1 [60-90 mins]). Participants will receive a PayCard in the mail following the last preparation visit onto which compensation will be loaded for this and future visits. Details of each component are provided below.

RESET Intervention (Video Visit 2-3): A member of the research team will meet with the participant on a secure Zoom Video Visit platform to conduct a total of 4 RESET intervention video visits. Each RESET intervention video visit will occur once or twice per week based on participant preference. The first intervention visit (Video Visit 2 [60 mins]) will include psychoeducation, interoceptive exposure (i.e., G6MW), and interoceptive counseling. At the end of Video Visit 2, participants will complete a series of valid, reliable, and pragmatic 4-item surveys designed to assess the acceptability, appropriateness, and feasibility of the RESET program, as well as the satisfaction of each intervention component and design feedback (e.g., psychoeducation, interoceptive exposure, interoceptive counseling. The other intervention visit (Video Visit 3 [30 mins]) will include interoceptive exposure (i.e., G6MW) and interoceptive counseling. At the end of the last intervention visit (Video Visit 3), participants will complete post-intervention questionnaires and an exit interview. Following the last intervention visit, additional compensation will be loaded onto the participant's PayCard. Details of each RESET intervention component are provided below.

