Post-Intervention (Video Visit 3 Continued and/or Phone Call 3): After completing the last RESET intervention visit (Video Visit 3), participants will be asked to complete the post-intervention questionnaires (20 mins), which will take place on the same secure Zoom Video Visit platform as Video Visit 3 or a at a separate date and time based on participant preference. Participants will also be asked to complete the semi-structured exit interview, which will take place via telephone (Phone Call 3 [30 mins]). To accommodate participant preference, participants will be given the option to complete the exit interview phone call immediately following the last RESET intervention visit or at a separate day and time.

After all intervention sessions are complete, the participant will be given the option to keep their devices or receive a pre-paid package to mail back the devices.

3. Compensation

Participants will receive a Bank of America PayCard in the mail after successfully completing the initial/first video visit (60 minutes). Once they confirm receiving the PayCard with study personnel, \$50 will be uploaded to the card as compensation for the pre-intervention preparation video visit. Following successful completion of the intervention video visits (2 and 3), post-intervention questionnaires, and audio-recorded exit interview, they will be compensated an additional \$100 on the PayCard. Therefore, the total possible compensation for completing the study is \$150. All compensation is loaded onto one Bank of America PayCard registered specifically to the participant.

In addition, participants will be permitted to keep the study-provided heart rate monitor and physical activity tracker (Fitbit Inspire HR) upon completion of the study, which has an estimated value of \$100.00 when purchased as new.

4. Risks

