Statistical Design and Power for Proposed Pilot Study: The Reducing Exercise Sensitivity with Exposure Training (RESET) Study

NCT Number: NCT05099926

Document Date: 1/26/2024

Statistical Design and Power for Proposed Pilot Study: The Reducing Exercise Sensitivity with Exposure Training (RESET) Study

Aim 1. Evaluate the feasibility, acceptability, and appropriateness of a home-based reducing exercise sensitivity with exposure training (RESET) intervention among acute coronary syndrome (ACS) survivors.

Aim 1 will be tested by assessing the following endpoints:

1. Proportion of participants that complete a majority (>90%) of the intervention;
2. Proportion of participants who complete the outcome assessments upon program completion;
3. Proportion of participants that had a majority (>90%) of the intervention sessions administered as intended;
4. Proportion of participants who report scores ≥ 4 for their final rating of the intervention's feasibility;
5. Proportion of participants who report scores ≥ 4 for their final rating of the intervention's acceptability;
6. Proportion of participants who report scores ≥ 4 for their final rating of the intervention's appropriateness.

Statistical approach for Aim 1. In addition to computing the proportions listed above, we will conduct secondary analyses regarding measures 4, 5, and 6 (see above) as follows. A one-tailed t-test will be conducted comparing the mean for each scale against the comparison value of each 5-point scale's midpoint of 3.

Sample Size and power estimates are based on Aim 1. Although some have used pilot studies to estimate effect sizes for primary outcomes, we agree with leaders in our field who argue that effect size estimates from small pilot studies are too imprecise to meaningfully inform effect size assumptions of power analyses for larger, later stage studies. Therefore, we do not provide power calculations for the effects of our intervention on adherence and behavioral health outcomes. We will, however, use estimates from these studies (e.g., standard deviations, attrition rates) to help determine an appropriate sample size for a subsequent study that is adequately powered to detect meaningful improvements in measures of exercise sensitivity and physical activity levels.

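### The protocol states a total of four RESET intervention video visits, but it schedules two (Video Visits 2 and 3)

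*Protocol*

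**What the plan says.** In section 3 (Study Procedures) of the protocol, the RESET Intervention paragraph says that research staff will meet the participant by Zoom "to conduct a total of 4 RESET intervention video visits". Its heading covers Video Visits 2 to 3 only. It goes on to call Video Visit 2 the first intervention visit, and then says: "The other intervention visit (Video Visit 3 [30 mins]) will include interoceptive exposure (i.e., G6MW) and interoceptive counseling". It closes with: "At the end of the last intervention visit (Video Visit 3), participants will complete post-intervention questionnaires and an exit interview".

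The other places that identify the visits are:

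- **Study Design, Table 1.** Video Visit 1 is set-up. Video Visits 2 and 3 are the only rows labelled as intervention visits. The continuation of Video Visit 3 is labelled "Post intervention visit" and holds questionnaires.
- **Study Design, text.** The intervention visits are described as "Video Visits 2-3) will include psychoeducation (in Video Visit 2 only").
- **Study Procedures, Post-Intervention.** "After completing the last RESET intervention visit (Video Visit 3), participants will be asked to complete the post-intervention questionnaires".
- **Compensation.** "Following successful completion of the intervention video visits (2 and 3), post-intervention questionnaires, and audio-recorded exit interview" triggers the second payment.

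In the SAP, Aim 1 endpoint 1 is "Proportion of participants that complete a majority (>90%) of the intervention". Endpoint 3 applies the same >90% threshold to the intervention sessions delivered as planned. Neither endpoint says how many sessions there are or which visits they are.

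**The concern.** The total contradicts the paragraph in which it stands, as well as the rest of the protocol. The number of sessions is the dose of the intervention, and the purpose of this pilot is to judge whether that dose can be delivered and completed.

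The SAP leaves the session count to the protocol. Someone looking there for a denominator finds a single explicit numeral, and it is the wrong one. Used literally for endpoint 3, or for endpoint 1 if that is scored by session, it would fail a participant who attended every scheduled intervention visit.

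**Working it through.** **Step 1: try to reproduce the stated total of 4.** The input is the list of video visits in Table 1.

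| What is counted | Visits | Count |
|---|---|---|
| Rows labelled as intervention | Video Visits 2 and 3 | 2 |
| The same plus set-up | Video Visits 1, 2 and 3 | 1 + 2 = 3 |
| All video rows, with the continuation of Video Visit 3 as its own row | 1, 2, 3 and 3 continued | 4 rows, but only 3 visits |

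The last line reaches 4 only by counting a set-up visit and a questionnaire block as intervention visits. The protocol places set-up under pre-intervention preparation and the questionnaires under post-intervention. No Video Visit 4 or 5 appears anywhere. The figure of 4 is not reproduced.

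**Step 2: set the statements side by side.** Seven mentions agree with two visits, and one gives four.

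1. Table 1: two intervention rows.
2. Study Design text: Video Visits 2 to 3.
3. Heading of the RESET Intervention paragraph: Video Visits 2 to 3.
4. Same paragraph: a first visit (Video Visit 2) and, in the singular, the other one (Video Visit 3).
5. Same paragraph: Video Visit 3 is the last.
6. Post-Intervention paragraph: Video Visit 3 is the last.
7. Compensation: the intervention visits are 2 and 3.

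Items 5 and 6 give two only when combined with the statement that Video Visit 2 is first. Without them, five mentions still give two directly.

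**Step 3: effect on the >90% endpoints.** A participant's share is sessions completed (or delivered as intended) divided by the session count, and it must exceed 0.90.

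- Scheduled count, all visits attended: 2/2 = 100%, meets the threshold.
- Stated total, all visits attended: 2/4 = 50%, does not meet it.

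With 4 as the denominator, no participant following the schedule could exceed 50%. The endpoint would then be 0 of 30 = 0% whatever happened in the study.

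**Step 4: what >90% means with so few sessions.** With *k* units, missing one gives (*k* − 1)/*k*.

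| Units *k* | Share if one is missed | Needed to exceed 90% |
|---|---|---|
| 2 (Video Visits 2 and 3) | 1/2 = 50% | both |
| 3 (adding the Video Visit 1 practice session) | 2/3 = 66.7% | all 3 |
| 4 (the stated total) | 3/4 = 75% | all 4 |
| 5 (components: 3 in Video Visit 2, 2 in Video Visit 3) | 4/5 = 80% | all 5 |

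Under each of these counts the threshold means all of the units.

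**The case against.** The strongest reply is that nobody would be misled for long. Two is plainly intended, the SAP never uses the number 4, and an analyst who did use it would fail every participant and notice at once. The 2/4 score also presumes a rule that neither document states. Endpoint 3 measures fidelity and could be taken over sessions actually held, while endpoint 1 refers to the intervention as a whole and could be scored by component. The documents do not explain where the 4 came from, and each intervention visit is said to occur once or twice a week, which could loosely suggest repeats. Finally, the SAP's silence on its counting unit would be a gap even without the wrong number.

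Most of this stands as a limit on severity. The effect on the endpoints is conditional on a literal reading, and the sponsor should confirm the count. None of it makes the sentence right. The frequency wording cannot rescue 4, because the paragraph names Video Visit 3 as both the other visit and the last one. The SAP sentence is a clarification that would not justify a change on its own, but it belongs with the correction.

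**Conclusion.** The concern holds, as a minor internal inconsistency. The protocol's total of four intervention video visits is wrong as written, and the scheduled number is two. Confidence in this is high because it rests on a direct count from the current text.

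The consequence for the endpoints (100% becoming 50% for a fully adherent participant) assumes that the stated total is used as the denominator and that the endpoint is scored by session. For endpoint 1 the SAP does not say that it is. The sample size of 30 and the SAP's figures for patients to approach (75, 60 or 50) do not depend on the visit count.

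**What to change.** Have the sponsor confirm that two visits are intended. Then, in the RESET Intervention paragraph of the protocol's Study Procedures, change the total from 4 to 2.

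In the SAP, add one sentence under Aim 1: the sessions counted for endpoint 3, and for endpoint 1 if it is scored by session, are Video Visits 2 and 3, so that >90% means both. The same sentence can say whether endpoint 1 is scored by visit or by component, and that the Video Visit 1 practice session is not counted.

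The cost is one digit and one sentence, with no added visits, data, patients or analysis.

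### The second payment bundles treatment visits with final assessments, so completion is observed under contingent payment and early stoppers are neither scheduled nor paid to give final data

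*Protocol*

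**What the plan says.** Under Compensation, the protocol pays in two parts. The first $50 is "as compensation for the pre-intervention preparation video visit". The second is conditional: "Following successful completion of the intervention video visits (2 and 3), post-intervention questionnaires, and audio-recorded exit interview, they will be compensated an additional" $100. The section then says that "the total possible compensation for completing the study is" $150. It adds that "participants will be permitted to keep the study-provided heart rate monitor and physical activity tracker (Fitbit Inspire HR) upon completion of the study", with an estimated value of $100. No part-payment is described for a participant who meets some of the conditions.

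The RESET Intervention paragraph under Study Procedures describes the timing differently: "Following the last intervention visit, additional compensation will be loaded onto the participant's PayCard". It does not mention the questionnaires or the interview as conditions. The Post-Intervention paragraph schedules both of those after the last intervention visit, and lets either take place on a separate day.

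In the SAP, Aim 1 endpoint 1 is "Proportion of participants that complete a majority (>90%) of the intervention" and endpoint 2 is "Proportion of participants who complete the outcome assessments upon program completion". Neither document mentions the payment when defining or interpreting these endpoints. The SAP's sample size paragraph plans to use attrition rates from this work to help size the next study.

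**The concern.** Two issues follow from the bundle.

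First, adherence is one of the protocol's own examples of feasibility, and its rationale is that fearful ACS patients avoid exercise. A payment that depends on attending the exposure visits acts on the behaviour that endpoint 1 counts. With one arm, the effect of payment cannot be separated from the acceptability of the visits. An attrition rate carried into the next sample size would inherit the same condition without saying so.

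Second, the people best placed to explain what went wrong are those who stop. As written, a participant who leaves after Video Visit 2 is not scheduled for the post-intervention questionnaires or the exit interview, and no payment is stated for doing them. Final ratings (endpoints 4 to 6), the exploratory change scores and the interview material on barriers would then come mainly from people who finished.

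**Working it through.** **1. Stated total.** $50 + $100 = $150, as the protocol says. The part that depends on the bundle is 100/150 = 67% of the cash. Counting the Fitbit at its stated $100, it is 200/250 = 80%.

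**2. Overlap with endpoint 1.** Table 1 and the Compensation section give two intervention visits (Video Visits 2 and 3). One of two is 50%, so exceeding 90% means attending both. If the intervention is counted in visits, everyone who earns the $100 meets endpoint 1. The RESET Intervention paragraph instead gives a total of 4 visits. Three of four is 75%, so the threshold would mean all four, and the payment condition would then name only two of them. The two counts must be reconciled, because they set the denominator of endpoint 1.

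**3. Overlap with endpoint 2.** The post-intervention questionnaires are a condition of the $100 and are also outcome assessments counted by endpoint 2. The endpoint's wording leaves open whether its denominator is everyone enrolled or only those who finished the programme.

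**4. Is the $100 visibly a bonus?** Durations from Table 1:
- Video Visit 2: 30 + 15 + (10 to 20) = 55 to 65 min
- Video Visit 3: 15 + (10 to 20) = 25 to 35 min
- Intervention total: 80 to 100 min
- Questionnaires and interview: 20 + (30 to 45) = 50 to 65 min
- Whole bundle: 130 to 165 min, so 100/165 × 60 = $36 to 100/130 × 60 = $46 per hour

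The $50 set against Video Visit 1 alone (60 to 90 min) is $33 to $50 per hour. Phone Call Visit 2 (50 to 60 min in Study Procedures) has no separate payment. If the $50 is spread over it as well (110 to 150 min), the rate is $20 to $27 per hour. The comparison depends on what the $50 is taken to cover.

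**5. Possible effect on endpoint 1 (assumption only).** Let d be the share of completers who would not have finished without the payment. Unpaid completion = observed × (1 − d). The documents give no value for d. For an assumed 27/30 = 90% observed (exact 95% interval 73% to 98%):

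| d | Unpaid completion |
|---|---|
| 0 | 90% |
| 0.1 | 81% |
| 0.2 | 72% |
| 0.3 | 63% |

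A single paid arm cannot locate the answer within that range, which includes no effect.

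**6. Completer-only final data (assumption only).** If m of 30 give a final rating and all m score at least 4, the observed proportion is 100%. Among all 30 it could lie anywhere from m/30 to 100%. For m = 27 the lower end is 90%, and for m = 24 it is 80%. Ratings are also collected at the end of Video Visit 2, so someone who stops after that visit has one. The SAP does not say whether it would count as the final rating.

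**7. When the payment is earned.** The Compensation section requires the exit interview, which may fall on a later day. The RESET Intervention paragraph has the money loaded after the last intervention visit. Where the interview is deferred, the two passages give different payment dates.

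**The case against.** A reader might infer that endpoint 1 measures paid attendance rather than feasibility. The documents do not support that. The SAP states the purpose as learning whether the team can recruit, retain and assess participants and deliver the intervention with fidelity, ahead of a larger randomized trial. Completion under ordinary trial compensation is evidence on that question, provided the later trial pays similarly. Adherence in an unpaid programme is not an Aim 1 endpoint. Feasibility does not rest on endpoint 1 alone either: endpoint 3, "Proportion of participants that had a majority (>90%) of the intervention sessions administered as intended", concerns delivery, and the payment does not depend on the ratings in endpoints 4 to 6.

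A reader might also infer that the $100 is an adherence bonus. It covers questionnaires and an interview as well as visits, and its hourly rate is close to that of Video Visit 1. Video Visit 2 also carries research surveys, so paying for visit time is defensible. That part of the objection stands, and it is why ending payment for visits is not asked for here. It does not answer the concern about contingency: the research tasks at the end cannot earn payment, as written, unless the treatment visits were attended.

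Three further points stand. The absence of part-payment is a silence in these two documents, and consent materials might fill it. The SAP sets no threshold for endpoint 1, so no stated decision turns on its value. Changing the payment alone would not bring in early stoppers' data, because the schedule does not offer them these assessments.

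**Conclusion.** The concern holds in a limited form. The payment condition coincides with endpoints 1 and 2, assuming that the intervention is counted in visits, that it consists of Video Visits 2 and 3, and that no part-payment applies. Completion should be read as completion with compensation. Any overstatement relative to unpaid use is plausible in direction, but the documents cannot give its size.

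The consequence that rests directly on the text is the gap in final data from early stoppers. Its size depends on how many stop: 3 to 6 of 30 (10% to 20%) under the assumed 27 to 24 completers. This is a worthwhile and inexpensive improvement. It does not undermine the pilot's ability to inform a similarly compensated trial.

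**What to change.** - **Payment.** Split the $100 so that the post-intervention questionnaires and the exit interview each carry their own payment, due whether or not Video Visits 2 and 3 were attended. Whether visit time is also paid can remain the sponsor's choice. State whether any part is pro-rated, and what happens to the Fitbit for someone who stops early.
- **Schedule.** Amend the RESET Intervention and Post-Intervention paragraphs so that both assessments are offered to participants who stop early.
- **Consistency.** Reconcile Study Procedures with Compensation on when the payment is earned, and reconcile the two counts of intervention visits.
- **SAP.** Report visit completion (endpoint 1) separately from assessment completion (endpoint 2), both in all enrolled participants. Describe endpoint 1 as completion with compensation, and say which rating counts as final for someone who stops early. Carry the attrition rate forward only to a trial with similar payment.

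The maximum per participant stays at $150. The added cost is up to $100 for each early stopper who gives data: $300 for 3 and $600 for 6, on the assumed numbers above. A small schedule and consent amendment is needed. The completion figures and ratings may come out less favourable.
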